9.7.4. IDMC

This study will use an independent data monitoring committee (IDMC).

The IDMC will monitor the safety of the SCTA01 during the trial on regular basis. The frequency and criteria to trigger the IDMC review is specified in the IDMC Charter.

The IDMC will be responsible for recommending the dose for Phase III part. The recommendations made by the IDMC to alter the conduct of the study will be forwarded to SCT for final decision. SCT will forward such decisions, which may include summaries of aggregate analyses of endpoint events and of safety data that are not endpoints, to regulatory authorities, as appropriate.

9.7.5. Interim Analyses

There will be three un-blinded interim analyses: the first IA is when the 143rd patient in Phase II has completed Day 8 visit; the second IA is at the end of Phase II; the third IA is when the 160th patient in Phase III has completed Day 29 or Early Withdraw visit. The timing of the third IA will be driven by the number of events accumulated in the Phase III part of the study, which is equivalent to about 31% of total number of events required in the Phase III part of the study.

Phase II: Two unblinded interim analyses are planned when the 143rd patient in Phase II has completed Day 8 visit. The preliminary review of efficacy data is supported if early data and external emerging data warrants. Given the event rate of 80%, 143 subjects would provide 80% power to detect a RR of 1.4 for a favorable outcome on TCCI for SCTA01 over placebo using a one-sided p-value of 0.2. Recommendations from the IDMC of no chance of success may be made but is not binding due to limited sample size. The 2nd interim analysis will be performed at the end of Phase II when the 285th patient has completed Day 29 or Early Withdraw visit. The purposes of this interim analysis are to select the dose for Phase III part of the study and check the futility of the study. The dose selected to continue to Phase III part will be the dose with a greater effect in reduction of viral load compared to placebo at Day 8 with no harmful effect on clinical improvement. Some other threshold, e.g. RR <1.2, may be used as a futility boundary at the end of Phase II. This more stringent than calculated futility boundary is set to control unwanted false positive rate. By applying calculated futility boundary from the design, the probability to claiming superiority of one dose in the end of trial is greater than 90% from the simulation. Considering the entirety of the data, if the IDMC observes an effect on viral load, study continuation may be recommended by the IDMC even if the futility bound is met on TCCI.

The stopping boundaries for efficacy and futility is displayed in the following table along with the stopping probabilities from simulation studies under assumptions for the effect of SCTA01 being harmful (RR = 0.9) or having no effect (RR = 1).

Table 7. Stopping Boundaries for Efficacy and Futility

	Events	Efficacy boundary (p-value)	Futility boundary	Cumulative probability of stopping under RR = 0.9	Cumulative probability of stopping under RR = 1
Interim 1(Safety review only)	NA	NA	NA	NA	NA
End of Phase II	149	NA	RR < 1.15	0.9385	0.8106
Interim 3	280	0.01068	RR < 1.22	0.9987	0.985
End of Phase III	556	0.0166	NA	0.9999	0.9897

Our simulation results suggest with the planned sample size and timing of interim analysis, under the hypothesis that SCTA01 is harmful (RR = 0.9) or has no effect (RR = 1), the probability of stopping the trial for applying a futility boundary of RR=1.15 is very probable with at least 81% probability, even at the early enrollment of the trial, e.g. the end of Phase II. Similarly, the probability of stopping the trial for applying a futility boundary of RR=1.2 is very probable with at least 88% probability.

Phase III: An unblinded interim analysis is planned.

The penultimate analysis, that allows for stopping the study for superior efficacy is planned when approximately 128 (31%) of the TTCI events have been documented in the Phase III ITT population. An α -spending function due to Lan DeMets (1983) with Pocock type stopping boundary will be used for the interim efficacy analysis. Therefore, if the interim analysis is done right after 280 events from Phase II and Phase III part have been documented, the combined *p*-value based on the inverse normal method of less than **1-side of 0.01068** will need to be observed to declare statistical significance. A futility boundary of an observed RR of 1.22 may be used to declare failure of the study when TTCI events from Phase II and Phase III part combined are exactly 280. Similarly, this more stringent than calculated futility boundary is set to control unwanted false positive rate. Note that the critical values of nominal *p*-value and hazard ratio needed to declare statistical significance at the interim analysis will be calculated based on the actual number of TTCI events documented at the time of the interim analysis.

An independent statistician external to the study team will perform the interim analyses and present the results to the IDMC. The IDMC will provide the Sponsor with a recommendation to continue the trial as planned, to have an interruption, to make a protocol amendment, or to terminate the trial. If the interim analysis demonstrates significant shorten TTCI in SCTA01 group compared to control group, the IDMC could recommend to terminate and un-blinded the study, and thus announce the study as completed.

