1.4. Primary Endpoints

- Time to clinical improvement (TTCI) up to Day 29. TTCI is defined as the time (in days) from randomization to the first day on which a patient satisfies Point 1, 2, or 3 on the 8-point ordinal scale¹ and maintains a score ≤ 3 at least 48 hours (initial improvement) and maintains this up to Day 29 (sustained improvement) (Phase II, III).

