3. INVESTIGATIONAL PLAN

3.1. Overall Study Design

The study is a multicenter, adaptive, randomized, double-blinded and placebo-controlled Phase II/III trial, and will be conducted at selected investigational sites globally.

Phase II part will evaluate the efficacy, safety, and PK of SCTA01 15 mg/kg, 50 mg/kg in patients with severe COVID-19. The primary endpoint will evaluate TTCI in study group 1 [SCTA01 15 mg/kg + best supportive care (BSC)], study group 2 (SCTA01 50 mg/kg + BSC) and control group (placebo + BSC) up to Day 29. The secondary endpoint will evaluate the virologic efficacy in study group 1 (SCTA01 15 mg/kg +BSC), study group 2 (SCTA01 50 mg/kg + BSC) and the control group (placebo + BSC) from baseline to Day 8, and then determine the recommended dose for Phase III part.

In the Phase II part of the study, 285 subjects will be randomized by 1:1:1 ratio to 15 mg/kg group, 50 mg/kg group and placebo group, with 95 subjects in each group.

At the end of Phase II part, enrollment will be paused and an interim analysis for dose selection will be performed after the 285th subject has been observed for TTCI. An IDMC will assess the benefit and risk to decide the dose for Phase III part of the part.

Enrollment will be resumed and the study continue into Phase III part after the IDMC has completed the evaluation and recommended the dose for Phase III part.

The Phase III part will evaluate the efficacy, safety, and immunogenicity of SCTA01 at the dosage recommended by the IDMC (X mg/kg or X mg) in severe patients with COVID-19. The primary endpoint will evaluate TTCI (8-point ordinal scale) in study group (SCTA01 X mg/kg or X mg + BSC) and control group (placebo + BSC) up to Day 29.

Approximately 510 subjects in Phase III part will be randomized by 1:1 ratio to SCTA01 (X mg/kg or X mg) and placebo, with 255 subjects in each group. The IDMC will be used to monitor safety and efficacy information.

Total number of subjects in the study is about 795.

Interim analysis (IA): There will be three un-blinded interim analyses when 143rd patient in Phase II has completed Day 8 visit, at the end of Phase II and when the 160th patient in Phase III has completed Day 29 or Early Withdraw visit.

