9.4. Sample Size

The treatment estimates are based on the study ACTT-1 of Remdesivir[®] for COVID-19. Under the TTCI definition used in this study, rate ratio (RR) for recovery for the severe patients, the patients with 5-point of baseline ordinal score and the patients with 6-point of baseline ordinal score is 1.31, 1.45 and 1.09 respectively^{31,32}. The event rate for the patients with 5-points is 88.8% and 76.8% for Remdesivir[®] group and placebo group, respectively. The assumption to calculate the sample size is set on the results from 5-points patients, which is RR as 1.4 and event rate as 80%. The sample size determination assumptions aim at a more meaningful clinical difference under a stricter TTCI definition.

Sample size is calculated based on the following assumptions:

- Overall Type-I error rate should not exceed 2.5% (1-sided);
- Rate ratio (RR) sets to be 1.4 (if the median TTCI is 9 days on the placebo group, the SCTA01 group will be 6.5 days under the assumption of Exponential distribution);
- Randomization ratio of study drug group and placebo group in Phase III is 1:1;
- Randomization ratio of medium dose group, high dose group and placebo group in Phase II is 1:1:1;
- 80% event rate;
- Sample size ratio of Phase II and Phase III is 1:1.79;
- Simes method will be applied to attain adjusted *p*-value from Phase II;

- Inverse normal weighting method will be used to combine *p*-value from Phase II and Phase III part;
- The 3rd interim analysis, which is the penultimate analysis for superior efficacy stopping and futility analysis, will be conducted when 31% of the TTCI events have been observed from the Phase III part;
- Pocock boundary (Lan DeMets 1983) will be used to control overall Type I error within 1-sided 2.5%;
- The critical values of nominal *p*-value will be re-calculated based on the actual number of TTCI events documented at the time of interim analysis and final analysis.

The study will randomize 795 patients totally, with Phase II of 285 patients and Phase III of 510 patients (255 in each group), providing over 90% power.

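### The 80% power quoted for the first interim assumes complete Day 29 outcomes and pooled doses, but the look is cut at the 143rd patient's Day 8 visit

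*Combined protocol and SAP*

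**What the plan says.** Section 9.7.5 fixes the timing: "the first IA is when the 143rd patient in Phase II has completed Day 8 visit". The same section gives a power for efficacy at that look, "Given the event rate of 80%, 143 subjects would provide 80% power to detect a RR of 1.4", on TTCI (printed there as TCCI) for SCTA01 over placebo, "using a one-sided p-value of 0.2". It lets the IDMC advise that there is no chance of success, and says such advice is not binding because the sample is small.

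The effect size and event rate are the planning values of Section 9.4: "which is RR as 1.4 and event rate as 80" (per cent). They belong to TTCI as defined in Section 1.4 and repeated in Section 9.7.1. That definition requires a score of 3 or better held "at least 48 hours (initial improvement) and maintains this up to Day 29 (sustained improvement").

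Phase II has three equal arms (Section 3.1): "285 subjects will be randomized by 1:1:1 ratio to 15 mg/kg group, 50 mg/kg group and placebo group".

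The documents describe the purpose of the look in different ways. Section 3.1 restricts it to safety data unless the IDMC asks for efficacy. The Synopsis and Section 9.7.5 support a preliminary efficacy review if early and external data justify it. Table 7 lists it as a safety review with no events and no boundary.

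**The concern.** An 80% event rate for an endpoint that has to hold to Day 29 is a rate at the end of follow-up. The power sentence applies it to all 143 patients at a moment when the last of them has reached only Day 8. The second and third interims do wait for the Day 29 or early-withdrawal visit. The first is the only look that pairs a Day 29 event rate with an earlier cut, and no provisional TTCI event is defined for it.

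What is at stake is how an IDMC would read a flat result. The permission to advise that there is no chance of success comes just after a quoted power of 80%. If the information at the cut is smaller than that, an uninformative result could be given more weight than it deserves.

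**Working it through.** **Inputs.** From Section 9.7.5: 143 subjects, event rate 80%, RR 1.4, one-sided level 0.2. From Section 3.1: allocation 1:1:1, so pooled SCTA01 to placebo is 2:1. From Table 4: Day 8 ± 1 and Day 29 ± 3, a nominal gap of 21 days. Accrual is not stated and is assumed uniform over a range of durations.

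**Formula.** With d events and allocation fractions p and 1 − p, power = Φ(ln 1.4 × √(d·p(1 − p)) − z), where ln 1.4 = 0.3365 and z = 0.8416. The factor p(1 − p) is 2/9 for 2:1 and 1/4 for 1:1.

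**Reproducing the plan's figure.** d = 143 × 0.8 = 114.4. At 2:1, √(114.4 × 2/9) = 5.042, and Φ(0.3365 × 5.042 − 0.8416) = Φ(0.855) = 80.4%. The stated 80% is reproduced.

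**Events needed for 80% at 2:1.** (2 × 0.8416 / 0.3365)² × 9/2 = 112.6, so 113. At an 80% rate, 113/0.8 = 141.25, so 142 of the 143 patients would need Day 29 status.

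**One dose against placebo, full follow-up.** Two thirds of 143 is about 95 patients and 76.3 events. Φ(0.3365 × √(76.3/4) − 0.8416) = Φ(0.628) = 73%.

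**Confirmed events at the Day 8 cut.** If the 143 patients accrue uniformly over A days, the fraction with Day 29 status is (A − 21)/A and d = 114.4 × (A − 21)/A.

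| Accrual of 143 patients (days) | Fraction with Day 29 status | Confirmed events | Pooled power |
|---|---|---|---|
| 30 | 30% | 34 | 53% |
| 60 | 65% | 74 | 70% |
| 90 | 77% | 88 | 74% |
| 120 | 82.5% | 94 | 76% |
| 180 | 88% | 101 | 77% |
| 365 | 94% | 108 | 79% |

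For example, at 60 days √(74.4 × 2/9) = 4.065 and Φ(1.368 − 0.842) = 70%.

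**Sensitivity: provisional improvements counted.** This takes the Section 9.4 medians (9 and 6.5 days, exponential), caps events at 80%, and counts improvements seen by the cut whether or not they are yet sustained. It gives about 108 to 113 events and 79–80% pooled power for accrual over 30 to 120 days. If all patients enrolled at once, it gives 70 events and 69%.

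**The case against.** The strongest reply is that little depends on this number. Efficacy review at the first look is optional, no efficacy or futility boundary is attached, and Section 9.7.5 itself warns that the sample is limited. Section 3.1 tells the IDMC to allow for the immaturity of the data unless they point to a conclusive outcome. All of this stands and limits the consequence.

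The second reply is that the shortfall depends on accrual. At slow accrual it is 1 to 3 points: 77.4% at 180 days, 79.0% at 365. A reader might infer from the Day 8 trigger that the look must be badly underpowered. The documents do not support that, because they give no accrual rate. What is certain is only that the full Day 29 event count is not available at the cut.

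Third, counting improvements provisionally would bring power back to about 79–80% for accrual over 30 to 120 days. That is correct, but it describes time to initial improvement, a separate secondary endpoint in Section 1.5. The sentence names TTCI.

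Fourth, pooling the doses is a fair reading of SCTA01 over placebo. A reader might take the 73% for one dose as proof that the 80% is miscalculated; it is not. The pooling is unstated, though, and Section 9.3 bases the confirmatory comparison on one selected dose, so it should be disclosed.

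**Conclusion.** The concern holds in a limited form. The arithmetic behind the 80% is sound for 143 patients with complete Day 29 outcomes and both doses pooled. It does not describe the data available when the 143rd patient reaches Day 8. On confirmed TTCI events, pooled power runs from about 53% to 79% for accrual over 30 to 365 days. That range assumes uniform accrual, an 80% event rate, RR 1.4, one-sided 0.2 and a 21-day gap; the visit windows move the gap by a few days without removing it.

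A reader might also infer that the error reaches the type I error rate, the later boundaries or the final power. It does not, since no decision rule at any later analysis uses this figure. This is a misstated power for an optional, non-binding review. It is worth correcting because it stands next to the permission to advise futility.

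**What to change.** In Section 9.7.5, take one of three routes:

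- (a) Replace the 80% with the power from confirmed TTCI events expected at the Day 8 cut, using the sponsor's own accrual projection and stating it. None of the accrual durations tabulated above should be written in, since none comes from the documents.
- (b) Name time to initial improvement as the efficacy endpoint for this look, and recompute power for the events observed by the cut.
- (c) Delete the power sentence.

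Whichever is chosen, reconcile Section 9.7.5 and the Synopsis with the safety-only description in Table 7 and the restriction in Section 3.1, so that the IDMC has one account of what is reviewed. If a figure is kept, say that it pools both doses and give the one-dose value beside it (about 73% even with full follow-up, lower at the cut).

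The cost is wording, plus a short recalculation under (a) or (b). Sample size, alpha and boundaries are unchanged. Under (a) the stated power becomes less favourable.

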9.7.6. Final Analysis

Final analysis will be performed when 556 TTCI events have been observed. A combined *p*-value based on the inverse normal weighting method of less than **1-side of 0.0166** will need to be

observed to declare statistical significance. The above derived boundaries are based on the assumption that the final analysis is performed when exactly 556 events are observed from both Phase II and Phase III part. If this assumption does not hold, the boundaries for *p*-value will be re-calculated according to the aforementioned α -spending function.

9.7.7. Sub-group Analyses

Subgroup analyses for the primary outcomes will evaluate the treatment effect across the following subgroups: country, race, ethnic group, duration of symptoms prior to enrollment, age, sex and comorbidity, best supportive treatment. A forest plot will display confidence intervals across subgroups. Interaction tests will be conducted to determine whether the effect of treatment varies by subgroups.

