9. STATISTICAL METHODS

9.1. General Principle

All statistical analyses will be done with the SAS software Version 9.4 or later. This is a double-blind, placebo controlled randomized trial with a one-sided Type I error rate of 0.025. Continuous variables will be summarized using descriptive statistics. Categorical variables will be summarized using frequency counts and percentages of patient incidence.

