9.3. Statistical Decision Rules

A combined *p*-value using inverse normal method of less than 1-side of 0.01068 from 3rd interim analysis or less than 1-side of 0.0166 from final analysis will need to be observed to declare statistical significance. The total number of patients in the ITT analysis sets for primary analysis will include patients in the recommended dose group in Phase II and in the same dose group that continued in Phase III, or the control group. i.e., 95 + 255 = 350 patients for recommended dose group or for control group. The patients from the inferior dose group (95 patients) in Phase II will only contribute to the multiplicity penalty of dose selection.

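### Study phase is missing from the subgroup list and the candidate strata, so no comparison of the treatment effect between the two combined phases is written down

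*Combined protocol and SAP*

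**What the plan says.** - **Subgroups (section 9.7.7).** Eight factors get a forest-plot row and an interaction test: "country, race, ethnic group, duration of symptoms prior to enrollment, age, sex and comorbidity, best supportive treatment". Study phase is not among them.
- **Strata (section 9.7.1).** The possible covariates for the stratified log-rank test are country, symptom duration, comorbidity and supportive treatment. Phase is not named. Sensitivity analyses are left to a SAP, with population, censoring rules and covariates given as examples. That SAP text is not in the supplied document.
- **Separate randomisation (sections 3.1 and 5.6).** Phase II is randomised 1:1:1 and Phase III 1:1. Recruitment stops between them until the Phase II outcomes are in: "At the end of Phase II part, enrollment will be paused and an interim analysis for dose selection will be performed after the 285th subject".
- **Success rule (sections 9.3, 9.7.2.1 and 9.7.6).** An inverse normal combination of a Simes-adjusted Phase II p-value (p1) and an unadjusted Phase III p-value (p2) must be below 0.01068 at the third interim analysis, or "less than 1-side of 0.0166 from final analysis will need to be observed to declare statistical significance". No minimum is set for the Phase III result.
- **Analysis set (section 9.3).** The primary comparison pools the phases: "i.e., 95 + 255 = 350 patients for recommended dose group or for control group".
- **Futility (section 9.7.5, Table 7).** The third-interim threshold, a rate ratio (RR) of 1.22, is also applied to events from both phases together. Table 7 gives no efficacy boundary at the end of Phase II.

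**The concern.** Rejecting the combined null hypothesis shows that the drug worked in at least one phase. It does not show that the effect was similar in both. The documents themselves give reasons why the phases could differ: enrolment is interrupted, background care follows local policy (section 3.6.2), vaccinated patients are eligible (section 4.1), and the Phase III dose may be weight-based or flat whereas the Phase II doses are weight-based only (section 5.2). The protocol also sequences the spike gene in non-responders (section 7.5), so it already treats viral change as relevant to response.

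At stake is interpretation. If the effect were mostly in the earlier phase, a single pooled estimate could be read as the effect of the selected dose under Phase III conditions, and nothing in the written analysis list would put the two phases side by side.

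**Working it through.** **Inputs.** Overall level: "one-sided Type I error rate of 0.025" (section 9.1). Design RR 1.4 and 80% event rate (section 9.4). Phase sizes: "with Phase II of 285 patients and Phase III of 510 patients (255 in each group), providing over 90% power" (section 9.4). Third interim: "approximately 128 (31%) of the TTCI events have been documented in the Phase III ITT population" (section 9.7.5). Selected dose plus placebo in Phase II: 95 + 95 = 190.

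**1. The plan's own figures reproduce.**
- Events: 0.80 × 190 = 152 in Phase II and 0.80 × 510 = 408 in Phase III, total 560 (stated 556). At the third interim, 152 + 128 = 280 (stated 280). Table 7 gives 149 for Phase II. Using 149 changes the results below by about 0.01 in RR.
- Interim boundary: 0.025 × ln(1 + (e − 1) × 0.31) = 0.010675 (stated 0.01068).
- Final boundary, from a bivariate normal with correlation √t at t = 128/408 = 0.314: 0.01660 (stated 0.0166), that is z = 2.130.
- Power at RR 1.4 with 556 events: ln(1.4) × √556 / 2 − 2.130 = 1.837, or 96.7%, consistent with the stated power of over 90%.

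**2. How Phase II and Phase III trade off at the final analysis.**
Weights are w1 = √(285/795) = 0.599 and w2 = √(510/795) = 0.801. Success needs 0.599 z1 + 0.801 z2 ≥ 2.130, with z = ln(RR) × √events / 2.
- p1 = 0.005: z1 = 2.576, so z2 = (2.130 − 0.599 × 2.576) / 0.801 = 0.73. Phase III RR = exp(2 × 0.73 / √408) = 1.075, p2 = 0.23. The Phase II RR behind that p1 is exp(2 × 2.576 / √152) = 1.52, or 1.58 if the Simes step doubles the p-value.
- p1 = 0.001: the Phase III RR needed is 1.035, p2 = 0.36. The Phase II RR is about 1.65 to 1.71.

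| Observed Phase III RR | p2 | p1 needed | Observed Phase II RR needed |
|---|---|---|---|
| 1.00 | 0.50 | 0.00019 | 1.78–1.83 |
| 1.05 | 0.31 | 0.0019 | 1.60–1.66 |
| 1.10 | 0.17 | 0.012 | 1.45–1.51 |
| 1.15 | 0.08 | 0.048 | 1.31–1.38 |

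The upper end of each range is the case where Simes doubles the p-value. If n1 in the weights is read as 190, the weights are 0.521 and 0.854, and the Phase II RR needed rises to 1.50–1.56 at a Phase III RR of 1.10, and to 1.94–1.99 at 1.00.

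**3. How often this matters.** Simulation used the closed test, a shared Phase II control, 76 events per Phase II arm, and a dose choice independent of time to clinical improvement (TTCI). The lower success rate in each range applies the futility stops; the higher one does not.
- True RR 1.4 in Phase II, 1.0 in Phase III: success in 20–22%.
- True RR 1.4, then 1.1: success in 41–47%. Of the successes at the final analysis, Phase III alone misses one-sided 0.025 in 73% with futility stops and 68% without.
- True RR 1.4 in both: about 0.6% of successes show a Phase III RR below 1.10.
- No effect in either phase: success in 1.0–1.6%, below 2.5%.

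**4. What a treatment-by-phase test could detect.** The standard error of the difference in log RR is √(4/152 + 4/408) = 0.190. At two-sided 0.05:
- 1.6 versus 1.0: ln(1.6)/0.190 = 2.47, power about 70%.
- 1.4 versus 1.0: 0.336/0.190 = 1.77, power about 42%.
- 1.4 versus 1.1: 0.241/0.190 = 1.27, power about 25%.
- 80% power needs a ratio of phase RRs of about 1.70.

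After a stop at the third interim the standard error is √(4/152 + 4/128) = 0.24, so power is lower still.

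**The case against.** Most of the case on the other side stands.

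- **The success rule, not the subgroup list, produces these results.** The success percentages in step 3 describe the inverse normal combination and would be identical after phase was added to section 9.7.7. They cannot be presented as the cost of the omission.
- **Validity is not at issue.** Each phase has its own concurrent randomised placebo group, so drift between phases does not bias p1 or p2. The pooled arms are also balanced within phase (95 and 95, then 255 and 255), so phase is not confounded with treatment. The Phase III-alone criterion used in step 3 is not one the protocol adopts.
- **Part of the check is already planned.** Section 9.7.2.1 needs p1 and p2 separately. Section 3.1 evaluates TTCI by dose in Phase II and states a Phase III TTCI comparison. Country and supportive treatment, through which some drift would show, are already in section 9.7.7. The SAP may add more.
- **The proposed test is weak** in the very scenarios that motivate it.

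A reader might infer that the trial can succeed on Phase II alone with no planned check. The documents do not support that. Table 7 allows no efficacy claim at the end of Phase II, and a Phase III RR of 1.00 to 1.05 passes only with an observed Phase II RR of about 1.6 to 1.8, against a planned 1.4.

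What the objection leaves open is narrower. Two p-values from phases of different size, one of them Simes-adjusted over both doses, are not effect estimates. No text sets the phase-specific RRs side by side, contrasts them, or names phase as a stratum.

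**Conclusion.** The point holds as a reporting and consistency gap, not as a flaw in error control. The analysis plan combines two separately randomised phases but names phase neither as a subgroup factor nor as a candidate stratum. A combined success can rest on a modest Phase III result: an observed Phase III RR of 1.10 (p2 = 0.17) passes with a Phase II RR of 1.45 to 1.51, not far above the design value. If the true effect is 1.4 in both phases this will be rare; if the effect fades it will not be, and the planned tables would not display it directly.

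This rests on 80% event rates, weights based on 285 and 510, the usual approximation for the variance of a log rate ratio under equal allocation, and the absence of phase from the supplied text. If the SAP already contains a by-phase comparison, a cross-reference closes the point.

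**What to change.** 1. Add study phase to the section 9.7.7 list.
2. Report the RR with 95% CI for the selected dose against concurrent placebo in each phase, beside p1, p2 and the combined p-value.
3. Give a treatment-by-phase test and label it descriptive, stating its standard error (about 0.19 at the final analysis) and its limited power, so that a non-significant result is not taken as proof of consistency.
4. Name phase as a stratum in Cox models fitted to the pooled phases, including the subgroup models, to match how patients were randomised.

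The cost is a few lines of SAP text and one low-power descriptive analysis. Boundaries, sample size, trial conduct and the success rule are unchanged.
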